# 3.3. Analysis

# 3.3.1. Intention-to-treat analysis

Effectiveness analyses of primary and secondary outcomes will be performed according to the intention-to-treat principle, i.e., we will include all participants that were included and randomized.

#### 3.3.2. Per-protocol analysis

The per protocol analysis will include adherent participants in the intervention group (defined as above in "3.2 Adherence").

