#### 2.3. Intervention

#### 2.3.1. Usual treatments provided by a physiotherapist

Participants in the control group will receive usual treatments provided by the physiotherapist. This includes any diagnostic procedure, treatment or referral the physiotherapist finds relevant based on the medical history, clinical findings and pragmatic, daily clinical practices to address musculoskeletal complaints. Participants are allowed to seek care and treatment elsewhere as they find relevant. After the completion of the long-term follow-up at 12 months, participants in the control group will be offered to use the app given to the intervention group.

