# 2.3.2. dCBT-I in addition to usual treatment provided by physiotherapists

Participants randomised to dCBT-I in addition to usual treatment provided by a physiotherapist will receive the sleep intervention delivered via a smartphone app. The trial will use a Norwegian dCBT-I programme named *Assistert Selvhjelp* (In English: 'Assisted Self-Help', website: https:// assistertselvhjelp.no/). The app consists of six interactive self-managing modules based on the principles from face-to- face CBT-I including sleep hygiene, stimulus control, sleep restriction, cognitive therapy, and relaxation training. Sleep restriction is covered in module 3, while both stimulus control and sleep hygiene are included in module 4. The modules also consist of tasks such as write sleep diary, practice sleep restriction and change lifestyle behaviour, learning material like quizzes and materials explaining and educating the patients about important aspects about sleep. These activities facilitate self-management and emphasize an active role in reducing insomnia symptoms. Patients will be recommended to use the app during the first six weeks after starting the physiotherapy treatment but are allowed to use the app in their own pace and during the whole project period. They will receive weekly notifications in the app.

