#### 3.2. Adherence

Sleep restriction and stimulus control are considered the most effective components in CBT-I (Furukawa, 2024). In the app, sleep restriction is covered in module 3, while stimulus control is included in module 4. Therefore, good adherence will be defined as completing at least the first four modules of dCBT-I. This will be defined based on the data on module unlocks.

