# 5.1.2. Analysis of primary outcome

In the primary analysis we will use linear mixed model analysis to estimate mean difference in ISI between the two groups at 3 and 6 months of follow-up, with 3 months as the primary endpoint for the outcome measurement. The model will include participant ID as a random effect. Time, group, and time-group interaction, will be used as fixed effects. Group means will be constrained to be equal at baseline due to the randomization (Coffman, Edelman & Woolson, 2016). Following evidence-based recommendations (Kahan & Morris, 2012; Kahan et. al., 2014), we will adjust for potentially important predictors of the outcome including age (years), sex (male vs female) and mean pain intensity level (0-10 scale). Unadjusted analysis will also be performed. The model assumptions for mixed models will be checked.

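### The per-protocol analysis selects dCBT-I participants on app use that controls cannot show, names no comparator or method for this, and leaves the adherence measure and its time window open

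*SAP*

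**What the plan says.** Section 3.3.1 puts the main analyses on all randomised participants: "Effectiveness analyses of primary and secondary outcomes will be performed according to the intention-to-treat principle". Section 3.3.2 then adds a second analysis in one sentence: "The per protocol analysis will include adherent participants in the intervention group". It refers back to section 3.2 for the meaning of adherent. It does not say which control participants are used, which outcomes and time points are analysed, which model is fitted, or how the result is to be interpreted.

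Section 3.2 states that "good adherence will be defined as completing at least the first four modules of dCBT-I". The reason given is that sleep restriction is covered in module 3 and stimulus control in module 4. The section closes with the data source: "This will be defined based on the data on module unlocks".

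Three other places bear on the point:

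- Section 2.3.1, on controls: "After the completion of the long-term follow-up at 12 months, participants in the control group will be offered to use the app".
- Section 2.3.2, on intervention participants, who "are allowed to use the app in their own pace and during the whole project period".
- Section 5.1.2, on the primary mixed model: "Group means will be constrained to be equal at baseline due to the randomization". The model also adjusts for age, sex and mean pain intensity.

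**The concern.** There are two separate problems.

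**Selection.** Whether someone works through four modules is decided after randomisation and is seen in one arm only. Controls do not get the app from the trial until after 12 months, so their would-be adherers cannot be identified and no matching subset can be formed. Any comparison of adherers with controls is therefore non-randomised. If people who persist with the app would have had different ISI scores anyway, that difference is counted as treatment effect. The equal-baseline constraint of the primary model rests on randomisation, and it loses that justification once one arm has been filtered.

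**Measurement.** Completing a module and unlocking one are different events. The SAP equates them without saying which unlock shows that module 4 was completed. It also sets no cut-off date, so modules reached after the 3-month assessment could make someone adherent for a 3-month outcome. This is exposure misclassification. It does not itself cause the mixing with prognosis.

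At stake is a pre-specified result that is easily taken as the effect in people who use the app, when the stated method does not identify that effect.

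**Working it through.** The SAP gives no figure for the per-protocol analysis, so there is none to reproduce. Its sample size supplies the scale for an illustration.

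**Step 1. Implied SD.** Section 2.4 gives 72 per arm, a 3-point difference, 90% power and two-sided alpha 0.05, but no SD. With the normal approximation for two means:

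SD = 3 / [sqrt(2/72) x (1.960 + 1.282)] = 3 / (0.1667 x 3.242) = 5.55 ISI points.

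**Step 2. Selection bias.** Let p be the share of would-be adherers. Let A and N be the mean untreated 3-month ISI of would-be adherers and non-adherers, and g = N - A. Randomisation gives the controls the same mix, so:

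- mean of all controls = pA + (1 - p)N
- untreated mean of the selected dCBT-I participants = A
- apparent benefit with no treatment effect = pA + (1 - p)N - A = (1 - p) x g.

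Neither p nor g is in the SAP; both are assumed below. A positive g means that adherers have the better prognosis. A negative g reverses the sign of the bias.

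**Step 3. False-positive rate with no treatment effect.** Take 72 controls, 72p adherers and SD 5.55. Then SE = 5.55 x sqrt(1/72 + 1/(72p)), and the two-sided rate is Phi(b/SE - 1.96) + Phi(-b/SE - 1.96), with b the bias from step 2. At p = 0.5 and g = 2: b = 1.0, SE = 5.55 x sqrt(1/72 + 1/36) = 1.13, b/SE = 0.88, and the rate is 0.14.

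| p (assumed) | g = 1 | g = 2 | g = 3 |
|---|---|---|---|
| 0.4 | 0.6 (8%) | 1.2 (17%) | 1.8 (31%) |
| 0.5 | 0.5 (7%) | 1.0 (14%) | 1.5 (26%) |
| 0.6 | 0.4 (7%) | 0.8 (12%) | 1.2 (20%) |
| 0.7 | 0.3 (6%) | 0.6 (9%) | 0.9 (14%) |

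Cells show the bias in ISI points and, in brackets, the false-positive rate against a nominal 5%. The calculation is unadjusted. If baseline ISI and the planned covariates are used, g is the gap that remains after them.

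**Step 4. The randomisation-based alternative and its weak point.** Let C be the effect in those who reach the exposure threshold and d the mean benefit in those who do not. The intention-to-treat effect is pC + (1 - p)d. The instrumental-variable estimate divides it by p:

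estimate = C + d(1 - p)/p.

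It is right only if d = 0. At p = 0.5 and d = 1 (both assumed) the four-module version overstates C by 1 x 0.5/0.5 = 1.0 point, as much as the selection bias at p = 0.5 and g = 2. A positive d is plausible at that threshold because module 3 already contains sleep restriction. If the threshold is having started the app, those below it have received no module, and d = 0 is credible.

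**Step 5. Precision.** Dividing by p stretches the confidence interval by about 1/p: 1/0.5 = 2.0, and 1/0.7 = 1.43. A low threshold raises p and so costs less.

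**Step 6. The unlock rule.** The app has six modules. If modules unlock in sequence, the unlock of module 4 shows that module 3 was finished, and the unlock of module 5 shows that module 4 was finished. The SAP does not describe the unlocking mechanism, so section 3.2 is compatible with either rule.

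**The case against.** The strongest reply is that section 3.3.2 is under-specified and not shown to be biased: it never says that adherers are compared with all controls. That is fair. The comparator is an inference, although a natural one. Without controls there would be no between-group estimate at all, and with any set of controls the comparison is non-randomised. The wording needs repair on every reading.

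A reader might infer that the bias favours dCBT-I. The SAP contains no adherence rate and no prognostic information on adherers, so neither direction nor size can be fixed. If the primary model is reused, baseline ISI is among its outcomes and age, sex and pain are adjusted for, so only the residual gap counts.

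A reader might also infer that merely opening module 4 makes someone adherent. Section 3.2 does not say so. It leaves open which unlock counts, and reading completion of module 4 from the unlock of module 5 would fit its words.

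It can further be objected that an instrumental-variable analysis at the four-module threshold may be as biased as what it replaces. Step 4 confirms this, which is why that threshold should not carry the main version. An analysis of 3-month ISI alone also gives up the repeated-measures likelihood on which section 5.3 relies for missing data, so it needs a stated missing-data method.

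Finally, the analysis is supportive only. That stands: the SAP gives the per-protocol result no role in the primary conclusion.

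**Conclusion.** The point holds as a defect of a supportive analysis that should be corrected before the data are analysed. Section 3.3.2 conditions on post-randomisation behaviour seen in one arm and offers no method to deal with it. On the natural reading the estimate is not a treatment effect, and the equal-baseline constraint is not justified in the selected subset. For adherence of 40% to 70% and a gap of 1 to 3 ISI points in favour of adherers, the bias would be 0.3 to 1.8 points against a design difference of 3. These inputs are assumptions; the figures show what is possible and are no evidence of what will happen. The adherence rule in section 3.2 is ambiguous on the qualifying event and silent on the time window. The documents do not support any doubt about the intention-to-treat primary result, the sample size or the primary error rate on this ground.

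**What to change.** 1. Replace section 3.3.2 by a complier average causal effect on ISI at 3 months. Use randomised arm as instrument for exposure, for example by two-stage least squares, and adjust for baseline ISI and the planned covariates. Trial-provided access is one-sided by design, because controls are offered the app only after 12 months.
2. Use a low exposure threshold, such as app started, as the main version. Report the four-module threshold as a sensitivity analysis, and state that it overstates the effect if users of fewer than four modules benefit.
3. Handle missing 3-month ISI by the multiple imputation already planned in section 5.3.
4. Count module 4 as completed by its completion record or, if modules unlock in sequence, by the unlock of module 5. Count only use up to the 3-month assessment.
5. If a comparison of adherers with controls is kept, name the control set and the model, label the result non-randomised, and drop the equal-baseline constraint.

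The cost is a revision of sections 3.2 and 3.3.2 and a short addition to the analysis syntax, including its combination with the imputed data sets. The statistical price is a wider confidence interval, by about 1/p, and an exclusion restriction that cannot be tested. No new data collection is needed beyond dated app records. Whether the app stores completion separately from unlocks should be confirmed first.

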#### 3.4. Blinding in statistical analyses and interpretation of results

Upon completion of data collection, patient data will be exported from the eForsk database. The project statistician will supervise the statistical analyses og both primary and secondary outcomes. The results will be presented graphically, excluding group labels, group size, and confidence intervals to the rest of the project group. The syntax for the main analyses will be prepared in advance and made available upon request.

# 4. Presentation of study population

#### 4.1. Screening data, eligibility, recruitment, and follow-up

[figure not shown]
Once the data collection is finalized, a CONSORT flow diagram will be created to show the number of participants that were screened, excluded (incl. reasons for exclusion), randomized and included, how many dropped out, how many participated in the different measurement timepoints and finally, how many finalized the data collection. See the CONSORT flow diagram in Figure 1.

#### 4.2. Withdrawal/Follow-up

All participants will be able to withdraw from the study at any time. The number of withdrawals in each group will be presented in the flow chart (Figure 1), including the reason for withdrawal if possible. Note that due to ethical considerations, participants are not obliged to explain their reason for withdrawing. Unless participants who drop out from the study explicitly request the removal of their data, the collected data will be used. If participants do not answer the questionnaire, they will be registered as 'lost to follow-up'. Lost to follow-up will be presented in a figure or in text.

# 4.3. Baseline patient characteristics

Descriptive statistics will be presented separately for the intervention and control group. Descriptive statistics will include age, sex, education level, employment status, physical and psychological health, medication and substance/alcohol use, sleep- and pain-related variables, and earlier treatment. Baseline values for primary and secondary outcomes (see 5.1 & 5.2) will be reported. Continuous data will be summarized as mean (SD) or median (interquartiles), depending on the distribution. Categorical data will be presented as numbers with percentages (%).

**Figure 1**: CONSORT flow diagram showing screening, allocation, and follow-up data.

#### 5. Analysis

#### 5.1. Primary outcome

# 5.1.1. Definition of primary outcome measures

The primary outcome measure is the participants' insomnia severity at 3 months follow up, assessed using the ISI (Morin et al., 2011). The ISI consists of 7 items, each scored on a 5-point scale. The composite score ranges from 0 to 28, with higher values indicating greater insomnia severity. For the primary analyses, ISI will be included as a continuous variable.

# 5.1.2. Analysis of primary outcome

In the primary analysis we will use linear mixed model analysis to estimate mean difference in ISI between the two groups at 3 and 6 months of follow-up, with 3 months as the primary endpoint for the outcome measurement. The model will include participant ID as a random effect. Time, group, and time-group interaction, will be used as fixed effects. Group means will be constrained to be equal at baseline due to the randomization (Coffman, Edelman & Woolson, 2016). Following evidence-based recommendations (Kahan & Morris, 2012; Kahan et. al., 2014), we will adjust for potentially important predictors of the outcome including age (years), sex (male vs female) and mean pain intensity level (0-10 scale). Unadjusted analysis will also be performed. The model assumptions for mixed models will be checked.

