#### 2.4. Determination of sample size

Previous studies show that the intervention effect in ISI from baseline to after intervention was 2.8-4.7 points in the intervention group compared to the control group (Vedaa et al., 2020; Wiklund et al., 2022). We therefore estimated that a sample size of 144 (72 in each group) was necessary to detect a 3-point difference with 90% power and a 2-sided alpha level of .05. Previous RCTs of dCBT-I report sample attrition rates between 12% and 50%(Christensen et al., 2016; Vedaa et al., 2020). To allow for a 30% dropout rate a 3-months follow-up, we aim to include 188 participants (94 participants in each arm) to answer our primary aim.

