## 3. Statistical principles

# 3.1. Confidence intervals and p-values

Estimates will be presented as mean differences or odds ratios with 95% confidence intervals. All p-values will be two-sided, and the significance level will be set to 0.05. No formal adjustment for multiple testing for secondary endpoints is made, but the issue of multiple testing will be kept in mind when interpreting results.

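### The primary model names only a participant random effect, so if baseline ISI varies less than follow-up ISI the 3-month test would exceed its 5% type I error

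*SAP*

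**What the plan says.** Section 5.1.2 of the SAP uses a linear mixed model to "estimate mean difference in ISI between the two groups at 3 and 6 months of follow-up", with 3 months as the primary endpoint. Its only statement on covariance is "The model will include participant ID as a random effect". The mean structure follows: "Time, group, and time-group interaction, will be used as fixed effects", and then "Group means will be constrained to be equal at baseline due to the randomization". A constraint on baseline means requires baseline ISI to be a row of the outcome vector, so it falls under the same covariance model as the follow-up visits.

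No random slope, visit-specific variance, residual correlation structure or robust standard error is named. The one safeguard is "The model assumptions for mixed models will be checked", with no action attached and no alternative named. Section 3.1 sets the level: "All p-values will be two-sided, and the significance level will be set to 0.05". Section 5.2.1 carries similar models over to the continuous secondary outcomes. The sensitivity analysis in section 5.3 concerns missing values only.

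**The concern.** A single participant intercept with independent residuals implies compound symmetry: one variance at all visits and one correlation between all pairs. That is a strong assumption once baseline is an outcome. A trial that enrols people because they have insomnia may cut off the lower part of the baseline ISI distribution, while follow-up scores can spread freely. Baseline may also correlate less with follow-up than the follow-up visits do with each other.

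If so, two errors reinforce each other. The smaller baseline variance is pooled into the common variance used for the 3-month standard error. The common correlation also over-weights the chance baseline difference in the adjustment. The confidence interval becomes too narrow and the p-value too small for the single primary test, and for any continuous secondary outcome with the same pattern.

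**Working it through.** **Inputs from the SAP.** Two-sided level 0.05 (section 3.1). Baseline, 3-month and 6-month visits, with equal baseline means (section 5.1.2). A design "necessary to detect a 3-point difference with 90% power and a 2-sided alpha level of .05", with 72 per arm before dropout, 94 per arm recruited and 30% dropout (section 2.4).

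**Assumed inputs.** All SDs and correlations, and 35% missing at 6 months. Section 2.4 states no SD. Solving its sample size for one gives SD² = 72 × 3² / [2 × (1.960 + 1.282)²] = 30.8, so SD ≈ 5.55. This is used as the follow-up SD. The error rate depends only on the ratio of baseline to follow-up SD and on the correlations, not on the absolute SD.

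**Formulas (complete data, n per arm).** Let v be the mean of the three variances and ρ the mean covariance divided by v, which are the values the random-intercept fit settles on. With d₀ and dₜ the between-group differences at baseline and 3 months:

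- estimated effect = dₜ − ρ·d₀
- model variance = (2/n)·v·(1 − ρ²)
- true variance = (2/n)·(sₜ² − 2ρ·cov₀ₜ + ρ²·s₀²)
- type I error = 2·[1 − Φ(1.96 / R)], where R = √(true variance / model variance)

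**Step 1: reproduce the plan's 5%.** Take SD 5.55 at every visit and all correlations 0.6. The model term is 30.80 × (1 − 0.36) = 19.71. The true term is 30.80 − 2 × 0.6 × 18.48 + 0.36 × 30.80 = 19.71. So R = 1 and the error is 5.0%: the level holds when compound symmetry is true.

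**Step 2: a narrower baseline.** Take baseline SD 4.0, follow-up SD 5.55, correlation 0.4 between baseline and follow-up, and 0.7 between 3 and 6 months.

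- v = (16.00 + 30.80 + 30.80)/3 = 25.87
- mean covariance = (8.88 + 8.88 + 21.56)/3 = 13.11, so ρ = 0.507
- model term = 25.87 × (1 − 0.507²) = 19.23
- true term = 30.80 − 2 × 0.507 × 8.88 + 0.507² × 16.00 = 25.91
- R = √(25.91/19.23) = 1.161, so the error is 2·[1 − Φ(1.688)] = 9.1%

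**Step 3: range of assumptions.** The dropout column is a large-sample calculation with data missing completely at random, 30% at 3 months and 35% at 6 months.

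| Baseline SD / follow-up SD | Correlations | Complete data | With dropout |
|---|---|---|---|
| 3.0 / 5.55 | 0.4 / 0.7 | 10.8% | 12.3% |
| 3.5 / 5.55 | 0.4 / 0.7 | 10.0% | 10.9% |
| 4.0 / 5.55 | 0.4 / 0.7 | 9.1% | 9.7% |
| 4.5 / 5.55 | 0.5 / 0.7 | 8.0% | 8.4% |
| 5.0 / 5.5 | 0.6 / 0.65 | – | 6.3% |
| 5.55 / 5.55 | 0.5 / 0.7 | 6.3% | 6.2% |
| 4.5 / 4.5 | 0.5 / 0.6 | – | 5.6% |
| 5.5 / 4.5 | 0.5 / 0.6 | – | 3.7% |

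In the first four rows with dropout, the true standard error exceeds the model's by 13% to 27%. With equal SDs, a wider grid of correlations on complete data gives 5.0% to 7.3%. Adding the 6-week visit with baseline SD 3 to 4 gives 8.2% to 11.8%.

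The restriction can also be produced by truncating baseline ISI at an assumed entry score. With dropout, the error is 8.2–8.6% at 8 or above, 9.4–10.1% at 12 or above, and 10.3–11.1% at 15 or above.

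**Step 4: effect of the remedy.** Null trials were simulated at 94 per arm with 30% dropout, correlations 0.4/0.7 and 1000 trials per case. At baseline SD 3.5 the random intercept gave 11.3% and an unstructured covariance 6.2%. At baseline SD 3.0 the figures were 10.8% and 4.6%. Simulation error around 5% is √(0.05 × 0.95/1000) ≈ 0.7 points, so the unstructured results are close to nominal.

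**The case against.** The strongest reply is that the SAP does not exclude a richer covariance. It names one component and is silent on the residuals, promises a check of assumptions, and says in section 3.4 that the syntax will be prepared in advance. That is fair, and it makes this an under-specification whose plain reading is compound symmetry. The check does not close the gap, because choosing a covariance after seeing the data is a decision the SAP is there to remove.

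The second reply is that the size rests on assumptions. This stands in full: the document gives no ISI entry cut-off, SD or correlation. The 5.55 is back-solved, and since section 2.4 describes an effect from baseline to after the intervention, it could be the SD of a change score. A reader might infer that the primary test will run at about 10%. The document does not support that: the error is about 6% under mild departures and 3.7% in the case where baseline varies more.

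Third, an effect of the design size would survive. With baseline SD 4, follow-up SD 5.5 and correlations 0.4/0.7, the true standard error with dropout is about 0.88, and 3/0.88 ≈ 3.4. The risk lies with a null or modest effect.

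A reader might also see a contradiction in listing group as a fixed effect while equalising baseline means. The constraint sentence settles this, because a free baseline group difference cannot be kept alongside it.

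Some limits remain. The planned adjustment for age, sex and pain was not simulated, nor was the robust fallback. No bias in the effect estimate under missing at random was computed, so none is claimed.

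**Conclusion.** The point holds as a conditional one and merits a should-fix. As written, the primary model most naturally means compound symmetry across baseline and follow-up. If selection for insomnia narrows baseline ISI to an SD of 3.5 to 4.5 against about 5.5 at follow-up, the 3-month standard error is too small and type I error is roughly 8% to 11%. With equal SDs it is about 5% to 7%, and it can be below 5% if baseline varies more than follow-up. Which case applies cannot be told from the SAP, and the plan commits to no action if the assumption fails.

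**What to change.** In section 5.1.2, replace the participant random effect with an unstructured residual covariance over visits within participant, fitted by REML with a named small-sample degrees-of-freedom method such as Kenward–Roger. In Stata `mixed` this is `noconstant residuals(unstructured, t(visit))` at the participant level. State the fixed effects as time and treatment-by-follow-up-visit, which builds in the baseline constraint.

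Name the fallback for non-convergence: a random intercept with standard errors clustered on participant, fitted by maximum likelihood if the software does not offer robust errors under REML. Apply the same wording to the continuous secondary outcomes in section 5.2.1, and make the change before allocation is revealed, in line with section 1.1.

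The cost is one paragraph and one line of code. Three visits need 3 × 4/2 = 6 covariance parameters and four visits need 4 × 5/2 = 10, against 2 now. That is modest for 140 to 188 participants, with a small risk of non-convergence that the fallback covers.
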